1.2.2.2 Phase 1 High-Dose Safety Study (GV29609)

In the Phase 1 high-dose Study (GV29609) 14 healthy volunteers were given single IV doses of placebo or MHAA4549A at 8400 mg (*Cohort A*) or 10800 mg (*Cohort B*) and followed for 120 days.

A total of 34 TEAEs were reported by 12 (85.7%) of the 14 subjects who received one dose of the study medication or placebo (safety population). Twenty-four (24) of these TEAEs were reported by 7 (87.5%) of the 8 subjects who had received MHAA4549A

and 10 TEAEs were reported by 5 (83.3%) of the 6 subjects who received placebo. TEAEs were reported by 3 of the 4 subjects receiving 8,400 mg MHAA4549A and 4 of 4 subjects receiving 10,800 mg MHAA4549A. No notable trends in types of TEAEs or laboratory results were observed between dose levels or between subjects who received MHAA4549A versus placebo.

The most commonly reported TEAEs were headache, reported by 4 subjects who received MHAA4549A (3 subjects in Cohort A and 1 subject in Cohort B), and nasopharyngitis, reported by three subjects who received MHAA4549A (1 subject in Cohort A and 2 subjects in Cohort B). All other TEAEs were each reported by no more than 1 subject who received MHAA4549A. The severity of TEAEs was primarily mild, with only three moderate TEAEs reported (a bacterial infection, observed in one subject who received 8400 mg MHAA4549A, and elevations of blood CK, observed twice in one subject who received 10,800 mg MHAA4549A). No serious adverse events or dose-limiting toxicities were reported.

No safety issues were observed with respect to vital sign results and ECG measurements. Overall, no relevant differences in mean values and changes or shifts from baseline over time were observed with respect to dose levels or MHAA4549A compared to placebo. No subjects in the study developed an ATA response following study drug administration.

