2. OBJECTIVES

2.1 PRIMARY OBJECTIVE

- To evaluate the safety and tolerability of a single IV dose of MHAA4549A as compared to placebo when administered in otherwise healthy patients with acute uncomplicated seasonal influenza A, focusing on the following:

Nature, frequency, and severity of serious and non-serious adverse events

Effects on laboratory values, vital signs, ECG parameters, and other safety biomarkers

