Appendix 1 Schedule of Activities

	Screening (-72 hours to 0 hours)	D1 ^a (Randomization)	D2	D3	D4	D5	D6	D7 (±1)	D8- 13	D14 (±2)	D30 (±7)	D100 (±7)	Unscheduled Visit	Early Discontinuation
Informed consent ^b	x													Complete all assessments for the current day. If a patient discontinues early after Day 7, only a telephone visit is required as the Early Discontinuation visit.
Rapid PCR test or rapid antigen test ^c	x													
Inclusion/exclusion criteria	x													
Medical history and demographics	x													
Seasonal influenza vaccine history	x													
Confirm onset flu symptoms	x													
Pregnancy screening ^d	x													
Concomitant medications ^e	x	x	x	x	x	x	x	x	x	x	x	x	x	
Vital signs ^f	x	x		x				x					x	
Electrocardiogram (12-lead) ^g	x	x ^h		x				x					(x)	
MHAA4549A/Placebo administration ⁱ		x												
Complete physical examination ^j	x												(x)	
Limited, symptom-directed physical examination/symptom assessment ^k		x		x				x					x	
Weight and height ^l	x	x		x				x					(x)	
Adverse events		x	x	x	x	x	x	x	x	x	x	x	x	
Hematology ^m	x			x				x					(x)	
Chemistry panel ^m	x			x				x					(x)	
Coagulation panel ^m		x												
Urinalysis ⁿ	x			x				x					(x)	
██████████ ██████████		x		x		x		x					(x)	

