Appendix 1 (cont'd) Schedule of *Activities*

	Screening (-72 hours to 0 hours)	D1 ^a (Randomization)	D2	D3	D4	D5	D6	D7 (±1)	D8- 13	D14 (±2)	D30 (±7)	D100 (±7)	Unscheduled Visit	Early Discontinuation
Influenza antibodies (HAI) ^p		x						x						Complete all assessments for the current day. If a patient discontinues early after Day 7, only a telephone visit is required as the Early Discontinuation visit.
Anti-MHAA4549A antibodies (ATA) ^p		x												
Serum for MHAA4549A PK measurements ^q		x		x		x		x					(x)	
████████████████████		x		x		x		x					(x)	
Telephone visit to assess safety			x							x	x	x		
Symptom Diary ^r		x	x	x	x	x	x	x	x	x				

AE= adverse event; D= day; HAI= hemagglutinin inhibition; PCR= polymerase chain reaction; PK= pharmacokinetic.

Notes: Days 1, 3, 5, 7, *unscheduled (shaded)*, and *early discontinuation (if applicable)* will be clinic visits.

Xs within parentheses, i.e., (X), indicate optional assessments.

Patients who are unable to return to the clinic should be contacted by phone to: 1) ascertain health status, 2) record adverse event information, and 3) ask that the diary be completed and returned.

^a All assessments on Day 1 should be performed prior to study drug administration.

^b Informed consent must be obtained from all patients.

^c Sample collection may involve a nasal swab or a nasopharyngeal swab, depending on the diagnostic platform *at the site*.

^d A urine pregnancy test should be collected only for women considered by the investigator to be of childbearing potential, see exclusion criteria. This result must be available within 48 hours prior to study treatment. If urine testing is not available at the site, blood already collected from an existing sample may be tested for pregnancy.

^e Concomitant medications should be recorded for 30 days prior to screening, through the study completion/early discontinuation visit. See exclusion criteria for prohibited therapies. Patients should report to study site all concomitant medications taken at home.

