Appendix 1 (cont'd) Schedule of *Activities*

- ^f Vital signs will be collected within 1 hour before MHAA4549A infusion and within 1 hour after completion of MHAA4549A infusion and include temperature (*oral*), respiratory rate, heart rate, systolic blood pressure, and diastolic blood pressure. Temperature should be measured using the same methodology throughout the study and should be measured prior to administration of any antipyretic drugs. Temperature, blood pressure, respiratory rate, and heart rate will be completed after the patient has been in a seated or supine position for at least 5 minutes.
- ^g Patient should rest in a supine position for 10 minutes prior. If screening ECG is taken within 1-3 hours pre-dose, Day 1 pre-dose ECG does not need to be taken.
- ^h On Day 1, ECG must be taken within 1-3 hours pre-dose and 1-3 hours post-dose.
- ⁱ All patients will be monitored for study drug reactions during administration and for at least 30 minutes after completion of study drug administration.
- ^j Complete physical examination includes evaluations of general appearance of head, eye, ear, nose, and throat, cardiovascular, dermatological, musculoskeletal, respiratory, gastrointestinal, genitourinary, and neurological systems. Changes from any prior examination should be recorded. New or worsened abnormalities should be recorded as AEs, if appropriate.
- ^k Limited, symptom-directed physical examination includes, at a minimum, evaluation of general appearance, dermatological examination of the injection sites, evaluations directed by patient-reported symptoms, and any other evaluations that the investigator deems clinically relevant. Changes from any prior examination should be recorded. New or worsened abnormalities should be recorded as AEs.
- ^l Height will be obtained at screening only. Weight will be obtained at all indicated visits (pre-infusion on Day 1). Height and weight will be recorded in centimeters and kilograms, respectively
- ^m Local laboratory measurements should be utilized. Hematology *and* chemistry panel at screening must be collected within 36 hours prior to study drug administration. Lipase will be reflexively assessed on all samples with amylase >ULN.

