Appendix 4 (cont'd)

DAID Toxicity Grading Tables for Laboratory Abnormalities

CHEMISTRIES				
	Grade 1	Grade 2	Grade 3	Grade 4
Hyperbilirubinemia (when accompanied by any increase in other liver function test)	1.1– < 1.25 × ULN	1.25– < 1.5 × ULN	1.5–1.75 × ULN	> 1.75 × ULN
Hyperbilirubinemia (when other liver function are in the normal range)	1.1– < 1.5 × ULN	1.5– < 2.0 × ULN	2.0–3.0 × ULN	> 3.0 × ULN

dL = deciliter; L = liter; mEq = milliequivalent; mg = milligram; ULN = upper limit of normal.

ENZYMES				
	Grade 1	Grade 2	Grade 3	Grade 4
AST (SGOT)	1.1– < 2.0 × ULN	2.0– < 3.0 × ULN	3.0–8.0 × ULN	> 8.0 × ULN
ALT (SGPT)	1.1– < 2.0 × ULN	2.0– < 3.0 × ULN	3.0–8.0 × ULN	> 8.0 × ULN
GGT	1.1– < 2.0 × ULN	2.0– < 3.0 × ULN	3.0–8.0 × ULN	> 8.0 × ULN
Alkaline Phosphatase	1.1– < 2.0 × ULN	2.0– < 3.0 × ULN	3.0–8.0 × ULN	> 8.0 × ULN
Amylase	1.1–1.5 × ULN	1.6–2.0 × ULN	2.1–5.0 × ULN	> 5.1 × ULN
Lipase	1.1–1.5 × ULN	1.6–2.0 × ULN	2.1–5.0 × ULN	> 5.1 × ULN
*CPK – mg/dL	1.25–1.5 × ULN	1.6–3.0 × ULN	3.1–10.0 × ULN	> 10 × ULN

ALT = alanine transaminase; AST = aspartase transaminase; CPK = creatine phosphokinase; dl = deciliter; GGT = Gamma-glutamyl transferase; mg = milligram; SGOT = serum glutamic oxaloacetic transaminase; SGPT = serum glutamic pyruvic transaminase; ULN = upper limit of normal.

URINALYSIS				
	Grade 1	Grade 2	Grade 3	Grade 4
Proteinuria	1+ or 200 mg–1 g loss/day	2–3+ or 1–2 g loss/day	4+ or 2–3.5 g loss/day	Nephrotic syndrome or > 3.5 g loss/day
Hematuria	Microscopic only < 10 RBC/hpf	Gross, no clots > 10 RBC/hpf	Gross, with or without clots, OR red blood casts	Obstructive or required transfusion
*Glucose	Trace	1+	2+	Hospitalization for hyperglycemia

g = gram; hpf = high power field; mg = milligram; RBC = red blood cell.

Appendix 5

Anaphylaxis Precautions and Management

Administration of MHAA4549A will be performed in a setting with emergency medical equipment and personnel who are trained to monitor for and respond to medical emergencies. A qualified physician *or medically qualified designee* will be on site during study drug administration for all patients.

The following equipment is needed in the event of a suspected anaphylactic reaction during study drug infusion:

- Airway management equipment
- O₂
- Epinephrine for subcutaneous, intravenous, and/or endotracheal use in accordance with standard practice
- Antihistamines
- Corticosteroids
- IV infusion solutions, tubing, catheters, and tape

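### In the main schedule PT and aPTT are drawn once, before dosing, so coagulation has a baseline but no scheduled post-dose value to compare between arms

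*Combined protocol and SAP*

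**What the plan says.** Section 2.1 includes this in the primary objective: "Effects on laboratory values, vital signs, ECG parameters, and other safety biomarkers". Section 3.4.1 makes graded clinical laboratory abnormalities part of the primary outcome. Table 2 (Section 4.5.7) lists PT and aPTT under coagulation, and Appendix 4 gives both a Grade 1 to 4 row.

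In Appendix 1 the row "Coagulation panel" has one mark, under Day 1. Footnote a reads "All assessments on Day 1 should be performed prior to study drug administration". Footnote m, attached to the row, says "Local laboratory measurements should be utilized" and gives no post-dose time for coagulation. Its 36-hour screening window names hematology and chemistry only.

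Appendix 2, for patients with recurrent influenza symptoms between Days 14 and 100, draws the same panel on Days 1, 3 and 7 of the recurrence.

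**The concern.** A laboratory test informs a drug-versus-placebo safety comparison only if it is measured after dosing in all arms. PT and aPTT are measured before dosing and then, for most patients, not again. The draw is not among the screening rows either, so it is not one of the screening evaluations that Section 4.5.1 requires before randomization. It is a baseline with no scheduled follow-up value to set against it.

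At stake is how an absence of findings is read. The report could show no treatment-emergent PT or aPTT abnormality simply because none was looked for. The unblinded committees, which under Section 3.1.4 judge whether toxicity is imbalanced between arms, would also have no scheduled coagulation data. Adverse event reporting does not fill the gap: under Section 5.3.5.5 a laboratory result must be verified by a repeat assessment before it has to be reported, and here no first post-dose test is planned.

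**Working it through.** **1. The schedule rows side by side (Appendix 1 unless stated).**

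| Panel | Screening | Day 1 | Day 3 | Day 7 | Unscheduled |
|---|---|---|---|---|---|
| Hematology | x | – | x | x | (x) |
| Chemistry | x | – | x | x | (x) |
| Urinalysis | x | – | x | x | (x) |
| Coagulation | – | x (pre-dose) | – | – | – |
| Coagulation, Appendix 2 (days of the recurrence) | n/a | x | x | x | n/a |

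**2. Is the Day 1 mark possibly post-dose?** Where a post-dose Day 1 measurement is wanted, a footnote says so. For ECG: "On Day 1, ECG must be taken within 1-3 hours pre-dose and 1-3 hours post-dose". The vital-signs and serum PK footnotes also give both a pre-dose and a post-infusion time. The coagulation footnote gives neither, so the general rule in footnote a applies and the draw is pre-dose.

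**3. Reproduce Table 5 (Section 6.1).** Inputs: n = 40 per arm, binomial. Formulas: P(at least 1) = 1 − (1 − p)^40; P(at least 2) = 1 − (1 − p)^40 − 40p(1 − p)^39.

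| True rate p | At least 1: computed (stated) | At least 2: computed (stated) |
|---|---|---|
| 1% | 33.1% (33%) | 6.1% (6%) |
| 5% | 87.2% (87%) | 60.1% (60%) |
| 10% | 98.5% (99%) | 92.0% (92%) |
| 15% | 99.9% (99%) | 98.8% (98%) |

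Every entry agrees within one percentage point, so the table is sound for any event that is actually observed in 40 patients per arm.

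**4. Apply it to PT and aPTT.** Scheduled post-dose draws in the main schedule: n = 0. P(at least 1) = 1 − (1 − p)^0 = 0% for every p. If the panel were drawn at Day 3 and Day 7, n returns to 40 and P(at least 1) is 33.1%, 87.2% and 98.5% at true rates of 1%, 5% and 10%. Here p is the chance that a patient shows a post-dose abnormality at either draw.

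**5. How much does Appendix 2 add?** The documents give no recurrence rate. Assume that 1% to 5% of 47 patients per arm enter Appendix 2. That is 47 × 0.01 = 0.5 to 47 × 0.05 = 2.4 patients per arm. With recurrence share r and p = 5%, P(at least 1 abnormality) = 1 − (1 − r × p)^47:

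- r = 1%: 1 − (0.9995)^47 = 2.3%
- r = 2%: 1 − (0.999)^47 = 4.6%
- r = 5%: 1 − (0.9975)^47 = 11.1%

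If all 47 were drawn post-dose, the figure would be 1 − (0.95)^47 = 91.0%.

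**The case against.** The strongest reply is that a baseline-only draw may be deliberate. Sections 1.2.2.1 to 1.2.2.3 describe no coagulation finding in any completed study. Section 1.2.1 says that the antibody's target is not expressed in human tissue without infection. The laboratory events seen most often in the challenge study (ALT, AST, amylase) are covered at screening, Day 3 and Day 7. Section 6.4 promises summaries of selected laboratory data only, and no passage commits to a post-dose PT or aPTT comparison. All of this is correct, and it limits the weight of the point: nothing here suggests a coagulation hazard, and no stated analysis is broken. It does not explain why Appendix 2 follows the same panel through Day 7, or what use the Day 1 value has for patients who never enter Appendix 2.

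Two stronger readings are tempting and do not hold.

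- A reader might infer that no patient will have any post-dose PT or aPTT value. That goes too far. Appendix 2 draws come after the original dose, in patients still exposed to a drug with a mean half-life of about 21.5 to 23 days (Section 1.2.3), and a clinician may order the test at any time. But Appendix 2 patients are selected after randomization and sampled during a new illness, at least 14 days after dosing.
- A reader might add creatine kinase (CK) as a second missing test, because it is not in Table 2, has a grade row in Appendix 4, and Section 1.2.2.2 reports "elevations of blood CK, observed twice in one subject who received 10,800 mg MHAA4549A". The documents do not carry this. In the other Phase 1 study the only CK event was on placebo, with none among 16 subjects on drug. The 10,800 mg dose is not used here. Appendix 4 is adapted from general tables and also grades fibrinogen, methemoglobin and magnesium, which Table 2 does not list. The list of samples sent to the Sponsor is blacked out, so it cannot be shown that CK is never measured.

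**Conclusion.** The point holds for coagulation only. The main schedule has no scheduled post-dose PT or aPTT draw, and none marked as optional at unscheduled visits, so these tests cannot contribute a randomized comparison to the primary laboratory-safety objective. The chance of seeing an abnormality from scheduled draws in the main schedule is 0% at any true rate, against 87.2% at a 5% rate with 40 patients per arm if the panel were drawn at Day 3 and Day 7. Under the assumed recurrence rates of 1% to 5%, Appendix 2 would supply roughly 0.5 to 2.4 patients per arm and a chance of about 2% to 11%, without a randomized contrast.

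This rests on three things: the single mark standing under Day 1, which can be confirmed against the formatted schedule; footnote a governing that mark; and 40 patients per arm having a post-dose draw, as Table 5 assumes. It is a cheap improvement, not a flaw that invalidates the trial. It is no evidence of a coagulation risk, and it does not extend to CK.

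**What to change.** Reconcile Appendix 1 with Appendix 2:

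- Mark the coagulation panel at Day 3 and Day 7, when hematology and chemistry blood is already drawn.
- Give it the same optional mark as the other panels at unscheduled visits.
- Keep the Day 1 pre-dose draw as the baseline; it already meets the Section 6.3 definition.
- State in Section 6.4 that PT and aPTT are among the laboratory data summarized by arm, graded by Appendix 4.

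The cost is one extra tube at each of two existing draws, plus local laboratory fees. No visit is added and the sample size does not change. If the Sponsor intends a baseline-only test, the protocol should say so and give the reason, and the study report should state that post-dose coagulation was not systematically assessed.

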Appendix 1 (cont'd) Schedule of *Activities*

	Screening (-72 hours to 0 hours)	D1 ^a (Randomization)	D2	D3	D4	D5	D6	D7 (±1)	D8- 13	D14 (±2)	D30 (±7)	D100 (±7)	Unscheduled Visit	Early Discontinuation
Influenza antibodies (HAI) ^p		x						x						Complete all assessments for the current day. If a patient discontinues early after Day 7, only a telephone visit is required as the Early Discontinuation visit.
Anti-MHAA4549A antibodies (ATA) ^p		x												
Serum for MHAA4549A PK measurements ^q		x		x		x		x					(x)	
████████████████████		x		x		x		x					(x)	
Telephone visit to assess safety			x							x	x	x		
Symptom Diary ^r		x	x	x	x	x	x	x	x	x				

AE= adverse event; D= day; HAI= hemagglutinin inhibition; PCR= polymerase chain reaction; PK= pharmacokinetic.

Notes: Days 1, 3, 5, 7, *unscheduled (shaded)*, and *early discontinuation (if applicable)* will be clinic visits.

Xs within parentheses, i.e., (X), indicate optional assessments.

Patients who are unable to return to the clinic should be contacted by phone to: 1) ascertain health status, 2) record adverse event information, and 3) ask that the diary be completed and returned.

^a All assessments on Day 1 should be performed prior to study drug administration.

^b Informed consent must be obtained from all patients.

^c Sample collection may involve a nasal swab or a nasopharyngeal swab, depending on the diagnostic platform *at the site*.

^d A urine pregnancy test should be collected only for women considered by the investigator to be of childbearing potential, see exclusion criteria. This result must be available within 48 hours prior to study treatment. If urine testing is not available at the site, blood already collected from an existing sample may be tested for pregnancy.

^e Concomitant medications should be recorded for 30 days prior to screening, through the study completion/early discontinuation visit. See exclusion criteria for prohibited therapies. Patients should report to study site all concomitant medications taken at home.

Appendix 1 (cont'd) Schedule of *Activities*

- ^f Vital signs will be collected within 1 hour before MHAA4549A infusion and within 1 hour after completion of MHAA4549A infusion and include temperature (*oral*), respiratory rate, heart rate, systolic blood pressure, and diastolic blood pressure. Temperature should be measured using the same methodology throughout the study and should be measured prior to administration of any antipyretic drugs. Temperature, blood pressure, respiratory rate, and heart rate will be completed after the patient has been in a seated or supine position for at least 5 minutes.
- ^g Patient should rest in a supine position for 10 minutes prior. If screening ECG is taken within 1-3 hours pre-dose, Day 1 pre-dose ECG does not need to be taken.
- ^h On Day 1, ECG must be taken within 1-3 hours pre-dose and 1-3 hours post-dose.
- ⁱ All patients will be monitored for study drug reactions during administration and for at least 30 minutes after completion of study drug administration.
- ^j Complete physical examination includes evaluations of general appearance of head, eye, ear, nose, and throat, cardiovascular, dermatological, musculoskeletal, respiratory, gastrointestinal, genitourinary, and neurological systems. Changes from any prior examination should be recorded. New or worsened abnormalities should be recorded as AEs, if appropriate.
- ^k Limited, symptom-directed physical examination includes, at a minimum, evaluation of general appearance, dermatological examination of the injection sites, evaluations directed by patient-reported symptoms, and any other evaluations that the investigator deems clinically relevant. Changes from any prior examination should be recorded. New or worsened abnormalities should be recorded as AEs.
- ^l Height will be obtained at screening only. Weight will be obtained at all indicated visits (pre-infusion on Day 1). Height and weight will be recorded in centimeters and kilograms, respectively
- ^m Local laboratory measurements should be utilized. Hematology *and* chemistry panel at screening must be collected within 36 hours prior to study drug administration. Lipase will be reflexively assessed on all samples with amylase >ULN.
- ⁿ *Urinalysis at screening must be collected within 36 hours prior to study drug administration.* Urinalysis includes pH, specific gravity, glucose, protein, ketones, blood, bilirubin, nitrite, and leukocyte esterase. Microscopic examination (e.g., sediment, RBCs, WBCs, casts, crystals, epithelial cells, bacteria) will be performed if clinically indicated. *Screening sample will be collected locally. Day 3, 7 and unscheduled samples will be collected locally and centrally.*
- ^o Day 1 serum PK samples are to be drawn *within* 30 (\pm 5) minutes pre-dose of MHAA4549A, and 60 (\pm 15) minutes after the end of infusion. On Days 3, 5, 7 PK samples will be drawn from the contralateral arm from that used for drug infusion and must be labeled with the exact time of draw.

Appendix 1 (cont'd) Schedule of *Activities*

- † The symptom diary and temperature (*oral*) should be completed two times daily: when *the study subject* first wakes up in the morning (before getting out of bed) and about 12 hours later, up to Day 14 or until resolution of symptoms (defined as a total symptom score of 0-1 for 24 hours without use of symptom relief medications). Temperature should be taken before administration of acetaminophen/paracetamol and/or NSAIDs. Day 1 entry will be completed within 6 hours prior to start of study infusion.

